#### 9.2 Setting

The overall source cohort will consist of all individuals aged 18 years or older as of the country-specific start dates.

The main cohort (i.e., the general population cohort) for objective #1-3 and #5-8 will consist of individuals who:

- 1) Are aged ≥50 years in Denmark and Sweden, ≥60 in Finland, and ≥65 in Norway (country-specific age cut-off for booster recommendations)
- 2) Have a known residency within the specific country
- 3) Have received AZD1222, BNT162b2, or mRNA-1273 vaccines only (AZD1222 as part of the primary vaccination course only)
- 4) Did not receive a booster (i.e., the third or fourth vaccine dose) within 90 days after the last received vaccine dose
- 5) Did not receive the fourth dose before the country-specific start dates (as this would indicate individuals who were particularly vulnerable to severe disease or individuals with immunocompromising conditions and thus would not be representative of the target general population)
- 6) No history of Covid-19 hospitalization prior to the country-specific start dates

Objective #3 will be evaluated in secondary cohorts consisting of individuals hospitalized for Covid-19 from the main cohort.

Objective #4 will be evaluated in secondary cohorts consisting of presumed immunocompromised individuals aged  $\geq$ 18 years. Immunocompromised will be defined as fulfilling at least 1 of the conditions in the table below:

Immunocompromised condition	Definition
Solid malignancy (1)	ICD-10 codes: C00–C80 (except C44) registered within 3 years
	prior to the index date

Hematologic malignancy (2)	ICD-10 codes: C81-C86, C88, C90-C96, D46, D47, D61.0, D70.0,
	D61.2, D61.9, D71 registered within 3 years prior to the index
	date
Rheumatologic or inflammatory disorder (3)	ICD-10 codes: D86, E85 [except E85.0], G35, J67.9, L40.1, L40.5,
	L93, L94, M05-M08, M30, M31.3, M31.5, M32-M35, M46
	registered within 3 years prior to the index date
Other intrinsic immune condition or	ICD-10 codes: B20, B21, B22, B231, B232, B24, B9735, D27.9,
immunodeficiency a (4)	D61, D72.8, D80, D81 [except D81.3], D82-D84, D89 [except
	D89.2], K70.3, K70.4, K72, K74.3-K74.6 [except K74.60 and
	K74.69], N04, 0987, R18, Z21, Z992 registered within 3 years
	prior to the index date
Organ or stem cell transplant (5)	ICD-10 codes: T86 [except T86.82-T86.84, T86.89, and T86.9],
	Z94, and Z98.85 registered within 3 years prior to the index date

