In secondary cohorts of individuals aged  $\geq 18$  years with presumed immunocompromised conditions, we will evaluate the effectiveness of the bivalent boosters received as the  $\geq 4$ th dose. We will utilize the same analytical matched approach as in the main analysis described above. Dependent on the data distribution, time of VE assessment may be day 180 or day 365 since booster vaccination. Similarly, dependent on data availability, we will further subgroup bivalent booster recipients according to booster received as fourth, fifth, or  $\geq$ sixth dose, and we will endeavour to assess similar subgroups as in the main cohort subgroup analyses including waning VE analysis. The VE estimates will be indirectly compared with the VE estimates from the main cohort analysis while stressing the limitations of such indirect comparisons.

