As we take confounders into account by matching to emulate a target trial that provides causal inference of the effectiveness of bivalent booster vaccination, our estimands represent the average treatment effect among treated, and, thus, results from the individual matched comparisons should primarily be interpreted separately. Consequently, an indirect comparison of for example VE among immunocompromised with VE in the general (immunocompetent) population is not ideal. Research questions such as "is the special vaccination schedule for immunocompromised, with shorter interval between doses and more vaccinations necessary?" and "does the special vaccination schedule for immunocompromised have the desired effect on VE?" are not straightforward and cannot be directly answered by use of our observational data. This would necessitate a comparison group of immunocompromised following the vaccination schedules of the general population and no overlap of such treatment strategies (i.e., vaccination programmes) exists within our real-world data due to the distinct vaccination recommendations set out for individuals with immunocompromised conditions by the national health authorities. However, if the size of the data allows, we will be able provide VE as well as waning effectiveness estimates among immunocompromised which can assist the evaluation of such study questions to some extent.

Given the broad inclusion within each Nordic country, our results will likely have a high degree of generalisability to other similar populations. However, our assessment of the comparative effectiveness of bivalent mRNA-booster vaccines given as a fourth dose against severe Covid-19 outcomes may only indirectly support any evaluation of the effectiveness of these vaccines within other Covid-19 vaccination schedule scenarios. Our findings may similarly not directly generalize to certain subpopulations not individually studied or to populations with a demographically different

composition. Such subpopulations include for example the general population younger than 50 years old or other specific clinical subgroups that were not studied.

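### The immunocompromised VE will be set against a main cohort described as immunocompetent, but that cohort's criteria keep people with five of the six immunocompromising conditions

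*Protocol*

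**What the plan says.** Section 9.2 defines the main cohort: "The main cohort (i.e., the general population cohort) for objective #1-3 and #5-8 will consist of individuals who" meet six criteria on age, residency, vaccine type, booster spacing, timing of the fourth dose and prior Covid-19 hospitalisation. Two of them bear on immune status, both through dose timing:

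- Criterion 4: "Did not receive a booster (i.e., the third or fourth vaccine dose) within 90 days after the last received vaccine dose".
- Criterion 5: "Did not receive the fourth dose before the country-specific start dates (as this would indicate individuals who were particularly vulnerable to severe disease". The same bracket gives immunocompromising conditions as a further reason.

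For the other cohort, "Objective #4 will be evaluated in secondary cohorts consisting of presumed immunocompromised individuals aged" 18 or over. Membership needs at least one of six conditions: five defined by ICD-10 codes in the three years before the index date (solid malignancy, haematologic malignancy, rheumatologic or inflammatory disorder, other intrinsic immune condition, transplant) and a sixth defined by vaccination pattern.

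In section 9.7, the paragraph on objective #4 states: "The VE estimates will be indirectly compared with the VE estimates from the main cohort analysis while stressing the limitations of such indirect comparisons". Section 9.9 labels the other side of that comparison when it says that "an indirect comparison of for example VE among immunocompromised with VE in the general (immunocompetent) population is not ideal". It gives two reasons for caution: each matched estimand is an effect among its own treated population, and vaccination programmes differ. It adds that no immunocompromised group following the general schedule exists in the data.

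**The concern.** A comparison of immunocompromised with immunocompetent people needs a comparator group without the immunocompromised. The main cohort is defined without reference to any immunocompromising diagnosis. Its propensity score includes cancer and autoimmunity-related conditions, so people with such diagnoses are expected in it. The protocol's caveats do not warn the reader that some people contribute to both estimates.

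Shared membership acts in one direction: it makes the two VEs look more alike than VEs from separate groups would. A small difference could then be read as showing that immune status matters little, when part of the similarity comes from counting the same people on both sides. The groups also differ in age range, dose number and possibly assessment day, which can move the difference either way.

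**Working it through.** The plan gives no figure on this point to reproduce. The check sets the two definitions in section 9.2 against each other.

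**Step 1. Which main-cohort criterion removes each condition?**

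| Immunocompromised condition | Removed from the main cohort by |
|---|---|
| 1 Solid malignancy | none |
| 2 Haematologic malignancy | none |
| 3 Rheumatologic or inflammatory disorder | none |
| 4 Other intrinsic immune condition | none |
| 5 Organ or stem cell transplant | none |
| 6, part 1: booster within 90 days of the last dose | criterion 4 |
| 6, part 2: fourth dose before roll-out | criterion 5 (roll-out is no later than the start date) |
| 6, part 3: fifth or later dose before study start | criterion 5 (a fifth dose implies an earlier fourth) |

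Condition 6 is removed in full; conditions 1-5 are not. Anyone with a code for conditions 1-5, above the country age limit, without a closely spaced booster, an early fourth dose or a prior Covid-19 hospitalisation, and given a bivalent fourth dose in the study period, qualifies for both cohorts.

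**Step 2. Are such people expected in the main cohort?** Yes. Section 9.7 puts cancer and autoimmunity-related conditions in the main-cohort propensity score. The Danish cancer covariate in section 9.3 (C00-C85 without C44, C88, C90-C96, three-year look-back) covers the codes of condition 1 and most malignancy codes of condition 2.

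**Step 3. Do the stated caveats cover this?** No. An effect among the treated and a difference in programmes are separate matters from shared membership. The statement in 9.9 that no immunocompromised people on the general schedule exist in the data sits badly with 9.2, whose criteria admit people with conditions 1-5 who followed that schedule.

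**Step 4. Other differences between the groups.** Age is 18 and over against 50, 60 or 65 and over by country (9.2). Dose is fourth or later against fourth only (target trial table, 9.1). Follow-up is 180 against 365 days in that table, while 9.7 leaves day 180 or 365 open for objective #4.

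**Step 5. Illustration of the dilution.** Let p be the share of the main cohort with conditions 1-5 and r their risk relative to the rest in the reference arm. Their share of reference-arm events is

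w = p·r / (p·r + 1 − p),

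and main-cohort VE = (1 − w)·VE(without conditions) + w·VE(with conditions). If VE with the conditions is the same in both cohorts, the observed contrast is (1 − w) times the contrast against a group without them. The documents give neither p nor r; both are assumed.

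| p | r | w | Contrast remaining |
|---|---|---|---|
| 3% | 1 | 3.0% | 97.0% |
| 5% | 2 | 0.10/1.05 = 9.5% | 90.5% |
| 10% | 2 | 0.20/1.10 = 18.2% | 81.8% |
| 10% | 3 | 0.30/1.20 = 25.0% | 75.0% |
| 15% | 4 | 0.60/1.45 = 41.4% | 58.6% |

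The last row needs both upper ends at once. Criteria 4 and 5 also remove those people with conditions 1-5 who had early or closely spaced doses, which lowers p by an unknown amount.

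**The case against.** The strongest reply is that little rests on this comparison. Objective #4 asks only for VE among immunocompromised people, and its comparators are other immunocompromised people in the same matched design. The cross-cohort comparison is one interpretive sentence, with no contrast statistic and no table or figure in the planned results of section 12. Section 9.9 says that the matched results should mainly be read separately. Keeping people with cancer or autoimmune disease in the main cohort is deliberate, because that cohort is meant to represent the population offered the booster. Section 9.7 also foresees, where data allow, subgroups of objective #4 by dose number and subgroups like those of the main cohort, which include age below 70 against 70 and over.

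Most of this stands, and it limits the point. A reader might infer that the main cohort is objective #4's own comparator, or that overlap biases the VE estimates themselves; the documents support neither. A reader might also infer that the judgement on the special schedule in 9.9 rests on this contrast. The text there refers to VE and waning among immunocompromised people, and only to a limited extent. Nor would restricting the immunocompromised side to fourth doses be a neutral repair: people qualifying under parts 2 and 3 of condition 6 would receive their bivalent booster as a fifth or later dose, so the restriction drops them and narrows the question.

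What the reply does not answer is the shared membership. The comparison is still promised, the label is still wrong, and neither the caveats nor the planned subgroups remove people with conditions 1-5 from the main-cohort side.

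**Conclusion.** The point holds for the indirect comparison in 9.7 and the limitation text in 9.9, and no further. The main cohort is a general population cohort from which only the dose-pattern condition has been removed; it is not immunocompetent. Its overlap with the objective #4 cohort pulls the two VEs together whenever VE truly differs by immune status.

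The size is unknown. Under assumed shares of 5-15% and relative risks of 2-4, the contrast would lose roughly 10-41%; with a share of 3% and no excess risk, about 3%. These figures assume equal VE for people with the conditions in both cohorts and are illustrations, not estimates. Age, dose and horizon differences add a distortion of unknown sign. The estimates for objectives #1-8 are not themselves biased by this, and the comparison is secondary and caveated, so this is an inexpensive improvement rather than a flaw in the study's main results.

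**What to change.** For this comparison only:

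- Estimate the comparator VE in main-cohort members with none of conditions 1-5 at the index date. Condition 6 is already excluded.
- Set it beside two immunocompromised estimates: the full objective #4 result, and the fourth-dose subgroup already foreseen in 9.7, restricted to the same country age limits and the same assessment day where data allow. Showing both avoids silently dropping people on the special schedule.
- Report, by country, how many people are in both cohorts.

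In the text, delete the word immunocompetent in 9.9, add shared membership to the limitations of the comparison, and reconcile the no-overlap statement in 9.9 with the criteria in 9.2. Keep the full main cohort for its own objectives.

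The cost is one extra run per country, using condition flags already needed for objective #4 and the common scripts described in 9.6, with lower precision in the restricted immunocompromised stratum.

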## 10. PROTECTION OF HUMAN PARTICIPANTS

No individual-level data will be shared between parties. Country-specific analyses are conducted on pseudo-anonymised data. All parties adhere to GDPR.

## 11. MANAGEMENT AND REPORTING OF ADVERSE EVENTS/ADVERSE REACTIONS

Not applicable. Secondary use of data.

#### 12. PLANS FOR DISSEMINATING AND COMMUNICATING STUDY RESULTS

Main results expected in the final study report:

- Tables of baseline characteristics before and after matching
- Figures of matching quality diagnostics
- Figures of cumulative incidences of severe Covid-19 outcomes until day 365 since day of fourth dose vaccination
- Tables of effectiveness estimates for all and by subgroups of the main study cohort
- Figures of waning VE for main study cohort (and immunocompromised study cohort if possible)
- Tables of association estimates for all and by subgroups of the all-cause mortality cohort
- Tables of effectiveness estimates for all and by subgroups of the immunocompromised study cohort

We anticipate multiple manuscripts, and findings will be reported to the general public by institutional press releases upon acceptance in academic peer-review journals or upon uploading to pre-print server (if decided relevant to do so).

We will adhere to the STROBE and ENCEPP guidelines when reporting results and drafting the manuscript(s).

Example of tables of main results:

	Country-combined measures of association (95% CI) at day 3 of follow-up				
	COVID-19 hospitalization COVID-19 deat			19 death	
	RD	CVE	RD	CVE	
4- vs 3-dose schedule analysis					
Fourth dose bivalent BA.1 boosted vs nonboosted					
All	XX (XX to XX)	XX (XX to XX)	XX (XX to XX)	XX (XX to XX)	
Strata					
Male	XX (XX to XX)	XX (XX to XX)	XX (XX to XX)	XX (XX to XX)	
Female	XX (XX to XX)	XX (XX to XX)	XX (XX to XX)	XX (XX to XX)	
<70 years					
≥70 years					
<6 months since last SARS-CoV-2 infection					
6-12 months since last SARS-CoV-2 infection					
>12 months since last SARS-CoV-2 infection					
<1 year between primary course and booster					
≥1 year between primary course and booster					
<1 year between first and second booster					
≥1 year between first and second booster					
BNT162b2 as fourth dose					
mRNA-1273 as fourth dose					
Fourth dose bivalent BA.4-5 boosted vs nonboosted					
All					
Strata					
Etc.					
Fourth dose monovalent (original) boosted vs nonboosted					
(additional comparison)					
All					
Strata					
Etc.					
4- vs 4-dose schedule analysis					
Bivalent BA.4-5 vs bivalent BA.1 boosted					
All					
Strata					
Etc.					
Bivalent BA.4-5 vs monovalent (OG) boosted (additional					
comparison)					
All					
Strata					
Etc.					
Bivalent BA.1 vs monovalent (OG) boosted (additional					
comparison)					
All					
Strata					
Etc.					

# **ENCePP Checklist for Study Protocols (Revision 4)**

Adopted by the ENCePP Steering Group on 15/10/2018

The European Network of Centres for Pharmacoepidemiology and Pharmacovigilance (ENCePP) welcomes innovative designs and new methods of research. This Checklist has been developed by ENCePP to stimulate consideration of important principles when designing and writing a pharmacoepidemiological or pharmacovigilance study protocol. The Checklist is intended to promote the quality of such studies, not their uniformity. The user is also referred to the ENCePP Guide on Methodological Standards in Pharmacoepidemiology, which reviews and gives direct electronic access to guidance for research in pharmacoepidemiology and pharmacovigilance.

For each question of the Checklist, the investigator should indicate whether or not it has been addressed in the study protocol. If the answer is "Yes", the section number of the protocol where this issue has been discussed should be specified. It is possible that some questions do not apply to a particular study (for example, in the case of an innovative study design). In this case, the answer 'N/A' (Not Applicable) can be checked and the "Comments" field included for each section should be used to explain why. The "Comments" field can also be used to elaborate on a "No" answer.

This Checklist should be included as an Annex by marketing authorisation holders when submitting the protocol of a non-interventional post-authorisation safety study (PASS) to a regulatory authority (see the Guidance on the format and content of the protocol of non-interventional post-authorisation safety studies). The Checklist is a supporting document and does not replace the format of the protocol for PASS presented in the Guidance and Module VIII of the Good pharmacovigilance practices (GVP).

countries	 	 
EU PAS Register® number:		

Study title: Effectiveness of bivalent Covid-19 booster vaccines in the Nordic

Sec	tion 1: Milestones	Yes	No	N/A	Section Number
1.1	Does the protocol specify timelines for				6
	1.1.1 Start of data collection 			$\boxtimes$	
	1.1.2 End of data collection 			$\boxtimes$	
	1.1.3 Progress report(s)				
	1.1.4 Interim report(s)				
	1.1.5 Registration in the EU PAS Register®				
	1.1.6 Final report of study results.				

Study reference number (if applicable):

<sup>1 Date from which information on the first study is first recorded in the study dataset or, in the case of secondary use of data, the date from which data extraction starts.

<sup>2 Date from which the analytical dataset is completely available.

Comm	ents:				
Sect	ion 2: Research question	Yes	No	N/A	Section Number
2.1	Does the formulation of the research question and objectives clearly explain:				7-8
	2.1.1 Why the study is conducted? (e.g. to address an important public health concern, a risk identified in the risk management plan, an emerging safety issue)	$\boxtimes$			
	2.1.2 The objective(s) of the study?	$\boxtimes$			
	2.1.3 The target population? (i.e. population or subgroup to whom the study results are intended to be generalised)	$\boxtimes$			
	2.1.4 Which hypothesis(-es) is (are) to be tested?	$\boxtimes$			
	2.1.5 If applicable, that there is no a priori hypothesis?				
Comn	nents:				
Sect	ion 3: Study design	Yes	No	N/A	Section Number
3.1	Is the study design described? (e.g. cohort, case-control, cross-sectional, other design)				9
3.2	Does the protocol specify whether the study is based on primary, secondary or combined data collection?				9
3.3	Does the protocol specify measures of occurrence? (e.g., rate, risk, prevalence)				9
3.4	Does the protocol specify measure(s) of association? (e.g. risk, odds ratio, excess risk, rate ratio, hazard ratio, risk/rate difference, number needed to harm (NNH))				9
3.5	Does the protocol describe the approach for the collection and reporting of adverse events/adverse reactions? (e.g. adverse events that will not be collected in case of primary data collection)	$\boxtimes$			11
Comr	nents:				
Sec	tion 4: Source and study populations	Yes	No	N/A	Section Number
4.1	Is the source population described?				9
4.2	Is the planned study population defined in terms of:				9
	4.2.1 Study time period				
	4.2.2 Age and sex				
	

4.2.3 Country of origin

4.2.4 Disease/indication

				
			-	*	

Sect	tion 4: Source and study populations	Yes	No	N/A	Section Number
	4.2.5 Duration of follow-up				9
4.3	Does the protocol define how the study population will be sampled from the source population? (e.g. event or inclusion/exclusion criteria)				9
Comn	nents:				
Sect	tion 5: Exposure definition and measurement	Yes	No	N/A	Section Number
5.1	Does the protocol describe how the study exposure is defined and measured? (e.g. operational details for defining and categorising exposure, measurement of dose and duration of drug exposure)	$\boxtimes$			9
5.2	Does the protocol address the validity of the exposure measurement? (e.g. precision, accuracy, use of validation sub-study)				
5.3	Is exposure categorised according to time windows?				9
5.4	Is intensity of exposure addressed? (e.g. dose, duration)				9
5.5	Is exposure categorised based on biological mechanism of action and taking into account the pharmacokinetics and pharmacodynamics of the drug?	$\boxtimes$			
5.6	Is (are) (an) appropriate comparator(s) [identified?				9
Comn	nents:				
Soci	tion 6: Outcome definition and measurement	Yes	No	N/A	Section
3ec	tion of outcome definition and measurement			11,72	Number
6.1	Does the protocol specify the primary and secondary (if applicable) outcome(s) to be investigated?				9
6.2	Does the protocol describe how the outcomes are defined and measured?				9
6.3	Does the protocol address the validity of outcome measurement? (e.g. precision, accuracy, sensitivity, specificity, positive predictive value, use of validation substudy)				9
6.4	Does the protocol describe specific outcomes relevant for Health Technology Assessment? (e.g. HRQoL, QALYs, DALYS, health care services utilisation, burden of disease or treatment, compliance, disease management)				
Comr	nents:				

Sect	ion 7: Bias	Yes	No	N/A	Section Number
7.1	Does the protocol address ways to measure confounding? (e.g. confounding by indication)	$\boxtimes$			9
7.2	Does the protocol address selection bias? (e.g. healthy user/adherer bias)				9
7.3	Does the protocol address information bias? (e.g. misclassification of exposure and outcomes, time-related bias)				9
Comm	nents:				
Sect	ion 8: Effect measure modification	Yes	No	N/A	Section Number
8.1	Does the protocol address effect modifiers? (e.g. collection of data on known effect modifiers, sub-group analyses, anticipated direction of effect)				9
Comn	nents:				
				·	
Sect	ion 9: Data sources	Yes	No	N/A	Section Number
9.1	Does the protocol describe the data source(s) used in the study for the ascertainment of:				9
	9.1.1 Exposure? (e.g. pharmacy dispensing, general practice prescribing, claims data, self-report, face-to-face interview)				
	9.1.2 Outcomes? (e.g. clinical records, laboratory markers or values, claims data, self-report, patient interview including scales and questionnaires, vital statistics)				
	9.1.3 Covariates and other characteristics?	$\boxtimes$			
9.2	Does the protocol describe the information available from the data source(s) on:				9
	9.2.1 Exposure? (e.g. date of dispensing, drug quantity, dose, number of days of supply prescription, daily dosage, prescriber)	Ø			
	9.2.2 Outcomes? (e.g. date of occurrence, multiple event, severity measures related to event)	$\boxtimes$			
	9.2.3 Covariates and other characteristics? (e.g. age, sex, clinical and drug use history, co-morbidity, co-medications, lifestyle)				
9.3	Is a coding system described for:				9
	9.3.1 Exposure? (e.g. WHO Drug Dictionary, Anatomical Therapeutic Chemical (ATC) Classification System)				
	9.3.2 Outcomes? (e.g. International Classification of Diseases (ICD), Medical Dictionary for Regulatory Activities (MedDRA))				
	9.3.3 Covariates and other characteristics?				-
9.4	Is a linkage method between data sources described? (e.g. based on a unique identifier or other)				9

Comm	ents:				
Sect	ion 10: Analysis plan	Yes	No	N/A	Section Number
10.1	Are the statistical methods and the reason for their choice described?				9
10.2	Is study size and/or statistical precision estimated?				9
10.3	Are descriptive analyses included?				9
10.4	Are stratified analyses included?				9
10.5	Does the plan describe methods for analytic control of confounding?				9
10.6	Does the plan describe methods for analytic control of outcome misclassification?				9
10.7	Does the plan describe methods for handling missing data?				
10.8	Are relevant sensitivity analyses described?				9
Comm	ents:				
		T		21/4	Castian
Sect	ion 11: Data management and quality control	Yes	No	N/A	Section Number
11.1	Does the protocol provide information on data storage? (e.g. software and IT environment, database maintenance and anti-fraud protection, archiving)	$\boxtimes$			9
11.2	Are methods of quality assurance described?				9
11.3	Is there a system in place for independent review of study results?		$\boxtimes$		
Comm	ents:				
Sect	ion 12: Limitations	Yes	No	N/A	Section Number
12.1	Does the protocol discuss the impact on the study results of:				9
